2.2. Specific objectives

The specific objectives of this study are to:-

- 1. Evaluate the nutrient profile of diets using proximate analysis.
- 2. Determine the nutritional status (i.e. stunting, wasting, underweight and overweight)of children diagnosed using anthropometric measurements.
- 3. Assess the dietary diversity score (DDS) of children using food frequencyquestioners (FFQ).
- 4. Examine the urine samples of children to identify the urine iodine (UI) level.
- 5. Assess the parents and caregivers perceptions about the Eating behaviour of ASD children using questioner.
- 6. Evaluate the ASD severity level and developmental growth of children with ASD in correlation to UI level.

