5.3. Weight

The children will be measured using an electronic weight scale with minimal clothing and no shoes and socks must be worn. The scale will be placed on a hard, flat (level) surface up on measurement and scale reading

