5.6. Food sample collection

50gm sample of food will be collected in sample collection bags from each meal consumed throughout the day by the researcher and legal guardians.

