6. ANALYSIS

6.1. Proximate analysis

- A) Moisture content: An Al-cup will be dried at 104°cfor 30 minutes and cooled in a desiccator, and record the weight (W1). 3 g of the sample will then be added in the Al-cup and weighed (W2). The sample will then be dried for two hours at 139 °C. Then, the final dried sample will be weighed (W3) and recorded after cooling in a desiccator. The net moisture content of the sample will then be calculated using the following formula. %MC= ((W2-W1)-W3) ×100/ W1-W3 (%MC = percentage of net moisture content, W1= weight of Al-cup, W2= weight of sample before drying, W3= weight of sample after drying.
- **B)** Crude protein: The amount of protein present is calculated using the Kjeldahl method of protein analysis. The food sample will be weighed (0.5-1g) into a digestion flask. The sample will then be digested by heating it in the presence of sulfuric acid, a catalyst, copper (0.5g), and potassium sulfate (100g). Digestion will convert any nitrogen in the food into ammonia, and other organic matter to C0₂ and H₂0. After the digestion has been completed the

digestion flask will be connected to a receiving flask by a tube. The solution in the digestion flask will be made alkaline by adding sodium hydroxide, which converts the ammonium sulfate into ammonia gas. The ammonia gas that is formed will be liberated and mixed with boric acid. The low pH of the solution will convert the ammonia gas into the ammonium ion, and will simultaneously convert the boric acid to the borate ion. The nitrogen content will then be estimated by titration of the ammonium borate formed with standard hydrochloric acid using a suitable indicator to determine the end-point. The following equations will be used to determine the nitrogen concentration of a sample and corresponding crude protein percentage. $\%N = \{(Vs - Vb) * molecular weight of N * N Hcl\}/sample weight*10, % protein = 6.25* %N (Vs= sample volume, Vb= blank volume, N Hcl = normality of Hydrochloric acid.)$

- C) Ash content: A cruisable will first be weighed on electronic balance (W1). Afterward, 3g of food sample will be measured using an electronic balance (W2). The samples will then be put on the hot plate and charred and will be placed in a muffle furnace for 2 hours at 550°c. The final weight will then be measured after cooling it down (W3). The ash content will then be calculated using the formula: Ash $\% = W3 W1 \times 100 W2$

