- D) Fat content (AOAC, 2000): Al-cup will first be heated for 30 minutes at 106°c, cooled on a desiccator, and weighed on electronic balance (W1). 1-5g of food sample will then be added on a thimble and weighed (W2). The thimble and Al-cup will be slot in the corresponding positions of the fat extraction unit. Subsequently, 70% of diethyl ether will be added to the sample in the thimble using a dispenser. The hot plate temperature will then be set at 500°cfor 20 minutes for soaking followed by the extraction step for 40 minutes. The third step will be the evaporation step. After the extraction step is complete, the extracted fat will be placed in an oven for 30 minutes at 106°c. The fat content will then be determined using the following formula (W3) % of fat= W3-W1 ×100 W2
- **E)** Total dietary fiber: duplicate portions will be incubated with pancreatic α- amylase and amyloglycosidase for 16 hr. at 370°c in a sealed 250ml bottle in shaking water. During this step, non-resistant starch will be solubilized and hydrolyzed to glucose and maltose by the combined action of the two enzymes. The reaction will then be terminated by PH adjustment and temporary heating. Protein in the sample will be digested with protease. For the measurement of high molecular weight dietary fiber, Ethanol or industrial methylated sprits

will be added and the insoluble and perceptible soluble dietary fiber will be captured, washed with ethanol and acetone, dried, and weighed. The final result will then be obtained by using the formula: Total dietary fiber (%) = (HMWDF+LMWSDF)/1000 (HMWDF = high molecular weight soluble dietary fiber LMWSDF= low molecular weight soluble dietary fiber)

6.2.Urine iodine analysis

Analytical methods consist of an initial digestion step to get rid of interfering substances, followed by the Sandell–Kolthoff reaction, of which the reading is obtained spectrophotometrically or colorimetrically. The digestion step will be held to remove Interfering substances in urine. The sample will be digested using the appropriate strong acid (e.g. ammonium persulphate). The oxidizing step will be carried out in a heated environment. The Sandell–Kolthoff reaction is a two-step reaction in which the rate of reaction will be measured during the reduction of the yellow-coloured ceric ions by arsenic in the presence of iodide to form colourless cerous ions and elemental iodine.

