6.3. Statistical analysis plan

Given the variability of the type of data generated from each assessment, data analysis and interpretation shall be done in the respective the nature of each data.

Anthropometric measurement data shall be analyzed using corresponding index of Weight for height, height for age, weight for age and MUAC for age and interpreted using international standards. ENA 2020 shall be used to record the measurements and convert to respective Z-scores.

The Data generated from CARS diagnosis will be on a scale from one (normal behavior) to four (severely abnormal behavior) for each category of questions. The scores between 30 and 37 indicate mild to moderate ASD, while scores between 38 and 60 indicate severe ASD. These results shall be analyzed by SPSS version 26 for descriptive statistics and correlations

In case of urine iodine analysis, the decrease in yellow color over a fixed period is measured by a colorimeter with an appropriate filter or with a spectrophotometer and plotted against a standard

curve constructed with known amounts of iodine. The resulting reading of iodine content shall then be compared among case and control groups of the study. SPSS version 26 shall be used to for descriptive statistics, significant difference and correlations

The data generated from proximate analysis of food samples shall be recorded for each analysis and calculated for average. The final figure represents the amount of nutrient present per 100 gm. thus amounts consumed by children. This data shall then be compared among case and control groups of the study. SPSS version 26 will also be used for descriptive statistics, significant difference and correlations

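### Section 6.3 treats nutrient content per 100 g as the amount the children consumed, but no section describes recording how much they ate

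*Combined protocol and SAP*

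**What the plan says.** The objective served by the proximate analysis is the first in section 2.2: "Evaluate the nutrient profile of diets using proximate analysis". This concerns composition; intake is not named.

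Section 5.6 describes the material: "50gm sample of food will be collected in sample collection bags from each meal consumed throughout the day". Section 6.1 turns laboratory weights into percentages of moisture, protein, ash, fat and fibre.

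Section 6.3 says the results are "recorded for each analysis and calculated for average", without saying what is averaged over. It then gives the interpretation: "The final figure represents the amount of nutrient present per 100 gm. thus amounts consumed by children". The next sentence sets up the group comparison: "This data shall then be compared among case and control groups of the study". Significance testing in SPSS follows.

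**The concern.** The second half of the interpretive sentence in 6.3 draws an intake conclusion from a concentration. The two agree only for a child who eats exactly 100 g. In a case-control comparison the intake ratio is the density ratio times the ratio of mass eaten, and the plan describes no record of the second factor.

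If the groups eat different amounts, a statement about consumption can be wrong in size or in direction even when every laboratory value is correct. The documents do not show whether the amounts differ. However, controls are matched on age and sex only (section 4.1), and the fifth specific objective studies eating behaviour in the ASD children. Equal mass eaten should not be taken for granted.

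**Working it through.** The plan gives no figure to reproduce here. The check has three parts.

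**1. Is mass eaten described anywhere?** Each place where a weight or dietary quantity appears:

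| Section | What is weighed or asked | Gives mass eaten? |
|---|---|---|
| 5.6 | A fixed 50 g from each meal | No: the same 50 g whether the portion is small or large |
| 5.3 | "The children will be measured using an electronic weight scale with minimal clothing" | No: body weight |
| 6.1 | Laboratory portions, for example 3 g for ash and 1-5 g for fat | No: analytical samples |
| 3 | Lists a weight scale and a food collection bag | No: no step for weighing meals is described |
| 2.2, objective 3 | Food frequency questionnaire, for the dietary diversity score | Not described: the form is not reproduced and nothing links it to the proximate data |

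The step from content to intake therefore has no described data behind it.

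**2. How far can content and intake diverge?** For one child:

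intake (g) = sum over meals of content (g/100 g) × mass eaten (g) / 100

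For a nutrient at an assumed 5 g/100 g, the intake is 5 g if 100 g is eaten. At assumed masses of 400, 600, 900 and 1200 g/day it is 20, 30, 45 and 60 g. One laboratory value thus covers a threefold range of intake.

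Between groups:

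intake ratio = density ratio × mass ratio

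The direction reverses when the mass ratio falls below 1 / density ratio. All ratios are case/control, and the density ratios are assumed:

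| Density ratio | Mass ratio below which direction reverses |
|---|---|
| 1.05 | 1/1.05 = 0.95 |
| 1.10 | 1/1.10 = 0.91 |
| 1.20 | 1/1.20 = 0.83 |
| 1.50 | 1/1.50 = 0.67 |

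At a density ratio of 1.20, assumed mass ratios of 0.67, 0.83, 1.00 and 1.25 give intake ratios of 0.80, 1.00, 1.20 and 1.50 (computed with 2/3 and 5/6 for the first two). In grams, cases at 10 g/100 g eating 500 g take in 10 × 500 / 100 = 50 g. Controls at 8 g/100 g eating 800 g take in 8 × 800 / 100 = 64 g. The group with the denser food has the lower intake.

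**3. Is the average at least the density of the diet?** Only if portions are equal, or if the average is weighted by portion. Suppose the average is an unweighted mean over meals, and both groups eat three meals at 12, 4 and 6 g/100 g. The mean is (12 + 4 + 6)/3 = 7.33 in each group, ratio 1.00. With assumed portions:

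- Cases, 100, 400 and 300 g: (100×12 + 400×4 + 300×6)/800 = 4600/800 = 5.75 g/100 g.
- Controls, 250, 300 and 250 g: (250×12 + 300×4 + 250×6)/800 = 5700/800 = 7.125 g/100 g.
- Ratio: 5.75/7.125 = 0.81.

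With equal portions both groups return to 7.33.

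**The case against.** The strongest reply is that little turns on this clause. The objective is composition, no intake variable or formula is planned, and what is tested is the averaged per-100 g figure, which suits that objective. The sentence is loosely written. Since the samples come from meals the children eat, it might mean only the nutrient content of the food consumed. The questionnaire may contain portion questions. The numerical examples are invented, and the averaging example depends on a choice the plan does not state: the average may be over laboratory replicates, as section 6.1 mentions duplicate portions for fibre.

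Much of this stands. The composition comparison is sound in principle and should be kept. The examples show what is possible, not what is likely. The averaging point is a secondary clarification. The claim about the questionnaire can only be that its use for portions is not described.

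It does not remove the error. The clause sits in the analysis plan, is the only statement of what the proximate result means, and comes immediately before the group comparison. Its natural reading is intake. If only composition was meant, deleting the clause loses nothing.

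One further point stands. Section 6.1 measures moisture but does not say whether the other nutrients are expressed on fresh or dry weight, so a corrected outcome name should state this.

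**Conclusion.** The concern holds. As written, section 6.3 leads to a conclusion on amounts consumed that the described data cannot support. What they support is a case-control comparison of nutrient content in the sampled meals.

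The fault lies in interpretation; the laboratory data remain usable for the first objective. It should be corrected before the results are interpreted. The size of any resulting error is unknown: it is nil if the groups eat equal mass, and otherwise equals the mass ratio as a multiplying factor. Small density differences are the most exposed, since a 5% difference reverses at a mass ratio of about 0.95. All densities, portions and masses used above are assumptions. The absence of any described record of mass eaten is read directly from the documents and does not depend on them.

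**What to change.** **Main change, section 6.3:**

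- Delete the part of the sentence that equates the per-100 g figure with consumption.
- Name the outcome as nutrient content in g per 100 g of sampled meals, and state fresh or dry weight.
- Limit the case-control conclusion to the composition of those meals.
- State the averaging: laboratory replicates first, then meals within child, with one value per child entering the comparison of 26 cases and 26 controls.
- Add that an unweighted mean over meals is not whole-diet density unless portions are equal.

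This is wording in one paragraph and needs no new data. The price is giving up any statement on amounts consumed.

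**Only if an intake conclusion is wanted:** add to section 5.6 the weighing of each sampled meal as served and of leftovers, allowing for the 50 g removed if it comes from the child's portion. For each child, compute the sum over meals of grams eaten × content / 100, and report it as intake on the sampled day, not usual intake. If the questionnaire does record portions, say so and say how they are used. This route adds work for the researcher or guardians at every sampled meal, which the documents do not allow to be quantified. Weighing by guardians also adds measurement error.

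### Nutrients per 100 g of food are compared as if they were intake, on an unstated weight basis and without using the measured moisture

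*Combined protocol and SAP*

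**What the plan says.** The first specific objective in section 2.2 is: "Evaluate the nutrient profile of diets using proximate analysis". Section 5.6 describes the sampling: "50gm sample of food will be collected in sample collection bags from each meal consumed throughout the day". Neither that section nor any other provides for weighing what the child ate. The food frequency questionnaire in section 2.2 is named only for the dietary diversity score.

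Section 6.1 lists five assays: moisture, crude protein, ash, fat and total dietary fibre.

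- **Protein** is expressed relative to the sample as weighed: "The food sample will be weighed (0.5-1g) into a digestion flask".
- **Ash and fat** each use W2, the weight of food taken (3 g for ash, 1 to 5 g for fat). No drying before weighing is described for these or for protein.
- **Fibre** has a formula with no sample weight in it.
- **Moisture** has its own formula, introduced by "The net moisture content of the sample will then be calculated using the following formula", and the result enters no other formula.

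Section 6.3 then gives the analysis: "The data generated from proximate analysis of food samples shall be recorded for each analysis and calculated for average". It continues "The final figure represents the amount of nutrient present per 100 gm. thus amounts consumed by children" and ends with the comparison: "This data shall then be compared among case and control groups of the study". It names no weight basis, no conversion to dry matter and no use of moisture as a correction. Carbohydrate and energy appear nowhere in the document.

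**The concern.** The text raises three separate matters.

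1. A content per 100 g becomes an intake only when multiplied by the weight eaten. Without that weight, a group comparison cannot show that one group consumed more or less of a nutrient.
2. As a comparison of composition, the result depends on the weight basis. On fresh weight, water dilutes the other components together. A group that happened to eat wetter food would look lower in protein, fat and ash at the same time, which is easily read as a general dietary deficit.
3. Carbohydrate by difference and energy could be obtained from the components already measured. Leaving them out makes the nutrient profile of objective 1 less complete and removes an energy-based comparison that water content does not affect.

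**Working it through.** The plan gives no expected nutrient value, moisture, standard deviation or power, so it has no figure of its own to reproduce. The check is an illustration with stated assumptions.

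**Inputs from the documents.** 26 cases and 26 controls (section 4); denominators and assays (section 6.1); comparison per 100 g (section 6.3).

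**Assumed inputs.** Identical dry composition in both groups: protein 12, fat 10, ash 4 and fibre 10 g per 100 g dry matter. Moisture 60% in one group and 62%, 65% or 70% in the other. Between-child SD of protein 1 to 3 g per 100 g. Energy factors 4, 9 and 4 kcal/g for protein, fat and available carbohydrate, with none for fibre.

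**Step 1: effect of water alone.** Nutrient per 100 g fresh = dry content × (100 − moisture)/100. The ratio between groups is therefore (100 − m2)/(100 − m1), whatever the dry content.

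| Moisture | Ratio | Shortfall | Protein | Fat | Ash |
|---|---|---|---|---|---|
| 60 vs 62% | 38/40 = 0.95 | 5% | 4.80 vs 4.56 | 4.0 vs 3.8 | 1.60 vs 1.52 |
| 60 vs 65% | 35/40 = 0.875 | 12.5% | 4.8 vs 4.2 | 4.0 vs 3.5 | 1.6 vs 1.4 |
| 60 vs 70% | 30/40 = 0.75 | 25% | 4.8 vs 3.6 | 4.0 vs 3.0 | 1.6 vs 1.2 |

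Dividing each value by its own (100 − moisture)/100 returns 12, 10 and 4 in both groups, so the difference is zero on a dry basis.

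**Step 2: could this reach significance?** For protein, SE = SD × √(2/26). The chance of a two-sided 5% result is about Φ(difference/SE − 1.96), a normal approximation for independent groups. With SD 1.5, SE = 0.416. At 60 vs 70% the difference is 1.2, and Φ(1.2/0.416 − 1.96) = 82%.

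| Assumed SD (g/100 g) | 60 vs 65% (difference 0.6) | 60 vs 70% (difference 1.2) |
|---|---|---|
| 1 | 58% | 99% |
| 1.5 | 30% | 82% |
| 2 | 19% | 58% |
| 3 | 11% | 30% |

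**Step 3: energy basis.** Available carbohydrate = 100 − moisture − protein − fat − ash − fibre.

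- At 60%: 100 − 60 − 4.8 − 4.0 − 1.6 − 4.0 = 25.6 g. Energy = 4 × 4.8 + 9 × 4.0 + 4 × 25.6 = 157.6 kcal per 100 g.
- At 70%: 100 − 70 − 3.6 − 3.0 − 1.2 − 3.0 = 19.2 g. Energy = 4 × 3.6 + 9 × 3.0 + 4 × 19.2 = 118.2 kcal per 100 g.
- Protein per 100 kcal: 4.8/157.6 × 100 = 3.05 g and 3.6/118.2 × 100 = 3.05 g. The difference disappears here too.

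**Step 4: can moisture be used as planned?** The formula in 6.1 A reads ((W2 − W1) − W3) × 100/(W1 − W3), taking the last two terms as the denominator. Take a 3 g sample with 60% true moisture (1.2 g left after drying) and an assumed 10 g cup:

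- W2 and W3 both with cup: (3 − 11.2) × 100/(10 − 11.2) = 683%.
- Both without cup: (3 − 10 − 1.2) × 100/(10 − 1.2) = −93%.
- W2 with cup, W3 without: (3 − 1.2) × 100/(10 − 1.2) = 20.5%.

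None of these readings returns 60%.

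**The case against.** **Fresh weight can be the intended quantity.** Wetter food does carry less protein and fat per 100 g as eaten, and no objective commits the study to dry composition or energy density. This stands, and it is why the per-100 g figures should stay. It does not rescue the step from content to consumption, and it does not excuse leaving the basis unnamed.

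**Moisture is itself a proximate result.** Under section 6.3 it would be compared between groups, so a difference in water could be seen. That is also fair. Seeing it next to the nutrients is still not the same as correcting for it.

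**Nothing suggests that the groups differ in moisture.** Correct. The documents contain no moisture value, and at a gap of 2 points the shift is only 5%.

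A reader might also infer more than the text supports:

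- *That every nutrient, fibre included, is on a fresh basis.* The inference is reasonable for protein, ash and fat. The fibre formula shows no sample weight, so its basis is unknown.
- *That the missing carbohydrate and energy cause the water effect.* They do not; the uncorrected weight basis does. Their absence only removes one comparison that would be free of it.
- *That omitting energy undermines the stunting and underweight objective.* Section 2.2 lists diet and anthropometry as separate objectives, and section 6.3 specifies no analysis linking them.

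**Conclusion.** The point holds as a limited one. The figures in section 6.3 describe composition and cannot be called consumption, because no weight eaten is recorded. This needs no assumption about moisture and would apply on either weight basis.

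The comparison of composition is open to a water effect that the plan measures but does not correct for. At identical dry composition the effect on protein, fat and ash is 5% to 25% for assumed group differences of 2 to 10 percentage points from 60%. With 26 children per group, the larger gaps could produce a significant protein difference from water alone, depending strongly on the assumed SD. This rests on reading the denominators in 6.1 as fresh weight. It shows what could happen and is not evidence that the planned comparison will be biased.

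The absence of carbohydrate and energy is a separate, minor gap in describing the nutrient profile. The whole point is a low-cost improvement and does not invalidate the study.

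**What to change.** Before any conversion, correct 6.1 A to: moisture % = (weight before drying − weight after drying) × 100 / weight of sample before drying, with the cup handled consistently in all weights. Check the fibre formula in 6.1 E, including its missing sample weight.

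Then, in section 6.3:

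1. State whether each per-100 g figure is on fresh or dry weight.
2. Delete the clause that equates the figure with what the children consumed, and describe it as food composition.
3. Report and compare protein, fat, ash and fibre per 100 g dry matter, alongside the per-100 g figures and moisture. For components measured on fresh weight, divide by (100 − moisture)/100, using the moisture of the same sample.
4. As a supplement, derive carbohydrate = 100 − (moisture + protein + fat + ash), available carbohydrate = that minus fibre, energy with stated conversion factors, and nutrients per 100 kcal.

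The cost is a few more derived variables and comparisons, and no new assay. Error in the moisture assay carries into the derived values. For example, an assumed overstatement of 1 percentage point raises a dry-basis figure by 40/39 − 1 = 2.6% at 60% true moisture and by 30/29 − 1 = 3.4% at 70%.
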